12. PROCEDURE FOR HANDLING PRODUCT QUALITY COMPLAINTS

A Product Quality Complaint (PQC) refers to any written, electronic, or oral communication that alleges deficiencies related to the identity, quality, durability, reliability, safety, effectiveness or performance of test articles after they have been released for clinical trial use.

Potential complaints may come from a variety of sources including but not limited to subjects, clinical research associates (CRA), clinical operations managers (COM), medical monitors, and site personnel, etc. The following are not considered product quality complaints:

- Subject satisfaction inquiries reported via “Subjective Questionnaires” and “Patient Reported Outcomes (PRO).”
- Clinical test articles that are stored improperly or damaged after receipt at the investigational site.
- Lens replacements that occur due to drops/fall-outs.
- Damage deemed by clinicians or clinical staff to be caused by handling by the user, and not indicative of a quality deficiency (i.e. tears, rips, etc.), only in situations where there is no deficiency alleged by the subject.

Within 24 hours of site personnel becoming aware that a PQC has occurred, the PQC must be recorded in the EDC system, which will trigger an automatic email notification to the appropriate COM/CRA and Clinical QA representative. In cases where the EDC system in use is not configured to send automatic notifications or when an EDC system is not used, the COM/CRA is responsible for notifying Clinical QA upon discovery that a PQC has occurred.

Upon receipt of the EDC notification, the COM/CRA will contact the study site to collect additional information which will include:

- Date the complaint was received/recorded in the EDC System (Date of Sponsor Awareness).
- Who received the complaint.
- Study number.
- Clinical site information (contact name, site ID, telephone number).
- Lot number(s).
- Unique Subject Identifier(s).
- Indication of who first observed complaint (site personnel or subject).
- OD/OS indication, along with whether the lens was inserted.
- Any related AE number if applicable.
- Detailed complaint description (scheduled/unscheduled visit, wear time, symptoms, resolution of symptoms, etc.).
- Eye Care Provider objective (slit lamp) findings if applicable.
- Confirmation of product availability for return (and tracking information, if available), or rationale if product is not available for return

Once a complaint is received, it will be assessed by the COM, CRA, or trained site personnel to determine if it is an Adverse Event/Serious Adverse Event (AE/SAE). If the complaint

Clinical Study Protocol

Johnson & Johnson Vision Care, Inc.

results in an AE/SAE, the COM/CRA, or trained site personnel will follow Section 13 of this protocol. If the AE/SAE was potentially the result of a product quality related deficiency, these procedures also apply and will be executed in parallel.

In some cases, a PQC form may be generated in EDC by the site in error. In this event, the PQC forms will be marked “Intentionally Left Blank” or “ILB”. Justification for ILB must be documented.

13. ADVERSE EVENTS

13.1. Definitions and Classifications

Adverse Event (AE) – An AE is “any untoward medical occurrence, unintended disease or injury, or untoward clinical signs (including abnormal laboratory findings) in subjects, users or other persons, whether or not related to the investigational medical device.”

Note: This definition includes events related to the investigational medical device or the comparator, and to the procedures involved. For users or other persons, this definition is restricted to events related to investigational medical devices.¹

An AE includes any condition (including a pre-existing condition) that:

1. Was not present prior to the study, but appeared or reappeared following initiation of the study.
2. Was present prior to the study but worsened during the study. This would include any condition resulting from concomitant illnesses, reactions to concomitant medications, or progression of disease states.

Note: Pregnancy must be documented as an adverse event and must be reported to the clinical monitor and to the Sponsor immediately upon learning of the event.

Serious Adverse Event (SAE) – An SAE is any adverse event that led to any of the following:

- Death
- Serious deterioration in the health of the subject that resulted in any of the following:
- Life-threatening illness or injury
- Permanent or persistent impairment of a body structure or a body function
- Hospitalization or prolongation of patient hospitalization
- Medical or surgical intervention to prevent life-threatening illness or injury or permanent impairment to a body structure or a body function.
- Chronic disease
- Foetal distress, foetal death or a congenital physical or mental impairment of birth defect.

Diagnoses and conditions that are considered Ocular Serious Adverse Events include, but not limited to:

- Microbial Keratitis (MK)
- Iritis (including cells in the anterior chamber)

Clinical Study Protocol

Johnson & Johnson Vision Care, Inc.

- Permanent decrease in best spectacle corrected visual acuity equivalent to 2 acuity lines or greater
- Central Corneal Opacity
- Central Corneal Neovascularization
- Uveitis
- Endophthalmitis
- Hypopyon
- Hyphemia
- Penetration of Bowman's Membrane
- Persistent Epithelial Defect
- Limbal cell Damage leading to Conjunctivalization

Significant Adverse Events – are defined as events that are symptomatic and warrant discontinuation (temporary or permanent) of the contact lens wear

Diagnoses and conditions that are considered Ocular Significant Adverse Events include, but not limited to the following:

- Contact Lens Induced Peripheral Ulcer (CLPU)
- Significant Infiltrative Events (SIE)
- Superior Epithelial Arcuate Lesions (SEALs)
- Any Temporary Loss of > 2 Lines of BSCVA
- Other grade 3 or higher corneal findings, such as abrasions or edema
- Non-contact lens related corneal events - e.g. Epidemic Keratoconjunctivitis (EKC)
- Asymptomatic Corneal Scar
- Any corneal event which necessitates temporary lens discontinuation > 2 weeks

Non-Significant Adverse Events – are defined as those events that are usually asymptomatic and usually do not warrant discontinuation of contact lens wear but may cause a reduction in wear time. However, the Investigator may choose to prescribe treatment as a precautionary measure.

Diagnoses and conditions that are considered Ocular Non-Significant Adverse Events include, but not limited to the following:

- Non-significant Infiltrative Event (NSIE)
- Contact Lens Papillary Conjunctivitis (CLPC)
- Superficial Punctate Keratitis (SPK)
- Conjunctivitis: Bacterial, Viral, Allergic
- Blepharitis
- Meibomianitis
- Contact Dermatitis
- Localized Allergic Reactions
- Any corneal event not explicitly defined as serious or significant adverse event, which necessitates temporary lens discontinuation < 2 weeks

Clinical Study Protocol

Johnson & Johnson Vision Care, Inc.

Adverse Device Effect (ADE) – An ADE is an “adverse event related to the use of an investigational medical device.”

Note 1: This definition includes adverse events resulting from insufficient or inadequate instructions for use, deployment, implantation, installation, or operation, or any malfunction of the investigational medical device.

Note 2: This definition includes any event resulting from use error or from intentional misuse of the investigational medical device.¹

Unanticipated Adverse Device Effect (UADE) – A UADE is any serious adverse effect on health or safety or any life-threatening problem or death caused by, or associated with, the test article, if that effect, problem, or death was not previously identified in nature, severity, or degree of incidence in the investigational plan, Investigator’s Brochure or protocol, or any other unanticipated serious problem associated with the test article that relates to the rights, safety and welfare of subjects.

13.2. Assessing Adverse Events

In conjunction with the medical monitor, the Investigator will evaluate adverse events to ensure the events are categorized correctly. Elements of categorization will include:

- Seriousness/Classifications (see definition in Section 13.1).
- Causality or Relatedness – i.e. the relationship between the test article, study treatment or study procedures and the adverse event (not related, unlikely related, possibly related, or related - see definition in Section 13.2.1).
- Adverse Event Severity – Adverse event severity is used to assess the degree of intensity of the adverse event (mild, moderate, or severe - see definition in Section 13.2.2).
- Outcome – not recovered or not resolved, recovering or resolving, recovered or resolved with sequelae, recovered or resolved, death related to adverse event, or unknown.
- Actions Taken – none, temporarily discontinued, permanently discontinued, or other.

13.2.1. Causality Assessment

Causality Assessment – A determination of the relationship between an adverse event and the test article. The test article relationship for each adverse event should be determined by the investigator using these explanations:

- Not Related- An adverse event that is not related to the use of the test article, study treatment or study procedures.
- Unlikely Related – An adverse event for which an alternative explanation is more likely, e.g. concomitant treatment, concomitant disease(s), or the relationship of time suggests that a causal relationship is not likely.
- Possibly Related – An adverse event that might be due to the use of the test article, or to the study treatment or study procedures. An alternative explanation, e.g. concomitant treatment, concomitant disease(s), is inconclusive. The relationship in time is reasonable. Therefore, the causal relationship cannot be excluded.

Clinical Study Protocol

Johnson & Johnson Vision Care, Inc.

- Related – An adverse event that is listed as a possible adverse effect (device) or adverse reaction (drug) and cannot be reasonably explained by an alternative explanation, e.g. concomitant treatment of concomitant disease(s). The relationship in time is very suggestive, e.g. it is confirmed by de-challenge and re-challenge.

13.2.2. Severity Assessment

Severity Assessment – A qualitative assessment of the degree of intensity of an adverse event as determined by the Investigator or reported to him/her by the subject. The assessment of severity is made irrespective of test article, study treatment or study procedure relationship or seriousness of the event and should be evaluated according to the following scale:

- Mild – Event is noticeable to the subject but is easily tolerated and does not interfere with the subject's daily activities.
- Moderate – Event is bothersome, possible requiring additional therapy, and may interfere with the subject's daily activities.
- Severe – Event is intolerable, necessitates additional therapy or alteration of therapy and interferes with the subject's daily activities.

13.3. Documentation and Follow-Up of Adverse Events

The recording and documenting of adverse events (ocular and non-ocular) begin when the subjects are exposed to the test article, study treatment or study procedure. Adverse events reported before the use of test article, start of study treatment, or study procedures will be recorded as medical history. However, if the condition deteriorates at any time during the study it will be recorded and reported as an AE. Untoward medical events reported after the subject's exit from the study will be recorded as adverse events at the discretion of the Investigator.

Upon finding an adverse event, the Principal Investigator will document the condition in the subject record and in the eCRFs and complete the Adverse Event eCRF.

Complete descriptions of all adverse events must be available in the subject record. All Adverse Events including local and systemic reactions not meeting the criteria for "serious adverse events" shall be captured on the appropriate case report form or electronic data system. All adverse events occurring while the subject is enrolled in the study must be documented appropriately regardless of relationship.

It is the Investigator's responsibility to maintain documentation of each reported adverse event. All adverse events will be followed in accordance with applicable licensing requirements. Such documentation will include the following:

- Adverse event (diagnosis not symptom).
- Drawings or photographs (where appropriate) that detail the finding (e.g., size, location, and depth, etc.).
- Date the clinical site was notified.
- Date and time of onset.
- Date and time of resolution.
- Adverse event classification, severity, and relationship to test articles, as applicable.

Clinical Study Protocol

Johnson & Johnson Vision Care, Inc.

- Treatment regimen instituted (where appropriate), including concomitant medications prescribed, in accordance with applicable licensing requirements.
- Any referral to another health care provider if needed.
- Outcome, ocular damage (if any).
- Likely etiology.
- Best corrected visual acuity at the discovery of the event and upon conclusion of the event, if the AE is related to the visual system.

Upon discovery of an AE that is deemed ‘possibly related’ or ‘related’ to the test article or study procedures (whether related to the visual system or not), an AE review form [REDACTED] must be completed. Additional dated and initialed entries should be made at follow-up evaluations. Separate forms must be completed for each eye if the AE is bilateral.

In addition, if an infiltrate(s) is present, he/she will complete the Corneal Infiltrate Assessment eCRF. Where necessary, a culture of the corneal lesion will be collected to determine if the infection is microbial in nature. If cultures are collected, the date of culture collection and laboratory utilized will be recorded.

Changes in the severity of an AE shall be documented to allow an assessment of the duration of the event at each level of intensity to be performed. Adverse events characterized as intermittent require documentation of the onset and duration of each episode. Changes in the assessment of relationship to the Test Article shall also be clearly documented.

Subjects who present with an adverse event shall be followed by the Investigator, within licensure, until all signs and symptoms have returned to pre-treatment status, stabilized, or been satisfactorily resolved. If further treatment beyond licensure is required, the patient will be referred to the appropriate health care provider. The Investigator will use his/her clinical judgment as to whether a subject reporting with an adverse event will continue in the study. If a subject is discontinued from the study, it will be the responsibility of the Investigator to record the reason for discontinuation. The Investigator will also document the adverse event appropriately and complete the Adverse Event eCRF. Any subjects with ongoing adverse events related to the test article, study treatment or study procedures, as of the final study visit date, should be followed to resolution of the adverse event or until referral to an appropriate health care provider, as recommended by the Investigator. Non-ocular adverse events that are not related to the test article, study treatment, or study procedures may be recorded as “ongoing” without further follow-up.

13.4. Reporting Adverse Events

The Investigator will notify the Sponsor of an adverse event by e-mail, facsimile, or telephone as soon as possible and no later than 24 hours from discovery for any serious /significant adverse events, and 2 days from discovery for any non-significant adverse event. In addition, a written report will be submitted by the Principal Investigator to the IEC/IRB according to their requirements (Section 13.4.2). The report will comment whether the adverse event was considered to be related to the test article, study treatment or study procedures.

Clinical Study Protocol

Johnson & Johnson Vision Care, Inc.

13.4.1. Reporting Adverse Events to Sponsor

Serious/Significant Adverse Events

The Investigator will inform the sponsor of all serious/significant adverse events occurring during the study period as soon as possible by e-mail or telephone, but no later than 24 hours following discovery of the event. The Investigator is obligated to pursue and obtain information requested by the Sponsor in addition to that information reported on the eCRF. All subjects experiencing a serious/significant adverse event must be followed up and all outcomes must be reported.

When medically necessary, the Investigator may break the randomization code to determine the identity of the treatment that the subject received. The Sponsor and study monitor should be notified prior to unmasking the test articles.

In the event of a serious/significant adverse event, the Investigator must:

- Notify the Sponsor immediately.
- Obtain and maintain in the subject's records all pertinent medical information and medical judgment for colleagues who assisted in the treatment and follow-up of the subject.
- Provide the Sponsor with a complete case history which includes a statement as to whether the event was or was not related to the use of the test article.
- Notify the IEC/IRB as required by the IEC/IRB reporting procedure according to national regulations.

Unanticipated (Serious) Adverse Device Effect (UADE)

In the event of an Unanticipated (Serious) Adverse Device Effect (UADE), the Investigator will submit a report of the UADE to the Sponsor and IEC/IRB as soon as possible, but no later than 24 hours after the Investigator first learns of the effect. This report is in addition to the immediate notification mentioned above.

The Sponsor must conduct an evaluation of the UADE and must report the results of the evaluation to FDA, the IEC/IRB and participating Investigators within 10 working days after the Sponsor first receives notification of the effect.

Non-Serious Adverse Events

All non-serious adverse events, including non-serious adverse device effects, will be reported to the sponsor by the Investigator no later than 2 days from discovery.

13.4.2. Reporting Adverse Events to the Responsible IEC/IRB and Health Authorities

Adverse events that meet the IEC/IRB requirements for reporting must be reported within the IEC/IRB's written guidelines. Each clinical site will refer to and follow any guidelines set forth by their Approving IEC/IRB. Each clinical site will refer to and follow any guidelines set forth by their local governing Health Authorities.

The Sponsor will report applicable Adverse Events to the local health authorities according the written guidelines, including reporting timelines.

Clinical Study Protocol

Johnson & Johnson Vision Care, Inc.

13.5. Event of Special Interest

None

13.6. Reporting of Pregnancy

Subjects reporting pregnancy (by self-report) during the study will be discontinued after the event is recorded as an Adverse Event. Once discontinued, pregnant participants and their fetuses will not be monitored for study related purposes. Pregnant participants are not discontinued from contact lens or solution related studies for safety concerns, but due to general concerns relating to pregnancy and contact lens use. Specifically, pregnant women are discontinued due to fluctuations in refractive error and/or visual acuity that occur secondary to systemic hormonal changes, and not due to unforeseen health risks to the mother or fetus.

14. STATISTICAL METHODS

14.1. General Considerations

Statistical Analysis will be undertaken by the sponsor or under the authority of the sponsor. A general description of the statistical methods to be implemented in this clinical trial is outlined below. More details will be included in the stand-alone Statistical Analysis Plan (SAP). The SAP will be developed and finalized prior to database lock.

All data summaries and statistical analyses will be performed using the Statistical Analysis System (SAS) software Version 9.4 or higher⁷ (SAS Institute, Cary, NC). Throughout the analysis of data, the results for each subject/eye will be used when available for summarization and statistical analysis. Unscheduled visits will be summarized separately and will be excluded from the statistical analysis.

Summary tables (descriptive statistics and/or frequency tables) will be provided for all baseline variables, efficacy variables and safety variables as appropriate. Continuous variables will be summarized with descriptive statistics (n, mean, standard deviation [SD], median, minimum and maximum). Frequency count and percentage of subjects or eyes within each category will be provided for categorical data.

Summaries will be presented by separately for each phase and lens type (O1D (Test) and P1 (Control)) and will be performed separately by completion status (Safety Population, Per-Protocol Population and Intent-to-Treat Population, when appropriate).

The interim analysis will be performed on the Per-Protocol population while the primary and secondary analyses for phase II will be performed on the Intent-to-Treat Population (see Section 14.3 for additional details).

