14.3. Analysis Populations

Safety Population:

All subjects who were administered any test article excluding subjects who drop out prior to administering any test article. At least one observation should be recorded.

Per-Protocol Population:

All subjects who have successfully completed all study visits and did not substantially deviate from the protocol as determined by the trial cohort review committee prior to database hard lock (Per-Protocol Population). Justification of excluding subjects with protocol deviations in the Per-Protocol Population set will be documented in a memo to file.

Intent-to-Treat (ITT) Population:

All randomized subjects regardless of actual treatment or deviation from protocol. At least one observation should be recorded.

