14.6. Secondary Analysis

All secondary items will be analyzed individually regardless of grouping and will model using the same model as described for the primary endpoints in Phase II above. Comparisons between O1D and P1 will be carried out using 1-sided 97.5% confidence intervals (CIs) constructed for the odds ratio (O1D over P1). For Secondary Group 1 – Comfort Performance and Secondary Group 2- Digital Device Performance, superiority of O1D relative to P1 will be concluded if the lower limit of the 97.5% CI is above 1. For Secondary Group 3 – Performance at Lens Fitting and Secondary Group 4- Lens Handling Performance, non-inferiority of O1D relative to P1 will be concluded if the lower limit of the 97.5% CI is above 0.67 (using 10% as non-inferiority margin and assuming a reference proportion of 0.5).

Note. $Aval$ will be derived as follows for Secondary Group 3 – Performance at Lens Fitting; $aval=1$ if a subject responds' 'Strongly Agree' or 'Agree', $aval=2$ if a subject responds' 'Neither Agree Nor Disagree' and $aval=3$ if a subject responds' 'Strongly Disagree' or 'Disagree')

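### The Phase II non-inferiority tests of lens handling (Group 4) rest on ITT alone, where protocol deviations can move the odds ratio towards 1; a Per-Protocol test should be required alongside.

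*Combined protocol and SAP*

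**What the plan says.** Section 14.1 of the combined protocol and SAP assigns analysis sets by phase. For Phase I, "The interim analysis will be performed on the Per-Protocol population"; for Phase II, "the primary and secondary analyses for phase II will be performed on the Intent-to-Treat Population". Section 14.3 defines ITT as "All randomized subjects regardless of actual treatment or deviation from protocol", with at least one observation recorded. It limits Per-Protocol to subjects who completed all visits and "did not substantially deviate from the protocol as determined by the trial cohort review committee".

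Section 14.6 makes Groups 3 and 4 non-inferiority tests (two insertion items and three handling items): "non-inferiority of O1D relative to P1 will be concluded if the lower limit of the 97.5% CI is above 0.67", each judged "using 1-sided 97.5% confidence intervals (CIs". It names no Per-Protocol test and no rule for agreement between sets. Apart from the interim analysis, 14.1 mentions the Per-Protocol set only for summaries, which "will be performed separately by completion status (Safety Population, Per-Protocol Population and Intent-to-Treat Population, when appropriate". The one sensitivity analysis, in 14.9, is multiple imputation if dropout exceeds 10%. That addresses missing data, not deviations.

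Section 2.2 places the Group 4 ratings at the 1-week follow-up and the Group 3 ratings at lens fitting. Table 5 in Section 10 lists 3 or more days without study-lens wear as a major deviation, with exclusion from Per-Protocol decided at cohort review.

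**The concern.** ITT is the cautious set for superiority, because ratings that do not reflect the assigned lens tend to hide a difference. In a non-inferiority test the same shrinkage helps the claim. If O1D were truly harder to handle by the full margin, and some handling ratings came from subjects who wore the wrong lens or barely wore the right one, the ITT odds ratio could sit above 0.67 for reasons that have nothing to do with the lens.

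The route is open in this trial. In Section 7.2, compliance is checked at steps 2.5 and 4.5, before the questionnaire at 2.7 and 4.7. Section 8.2 has discontinued subjects complete the current visit, so a poorly compliant subject's rating can still be collected and enter ITT. Under Sections 5.1 and 6.4, masked, over-labelled lenses are pulled by site staff from a fitting schedule, so a wrong-lens error is possible. On the ITT definition such a subject stays in.

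At stake is a confirmatory claim on three handling items that could owe something to poor adherence.

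**Working it through.** **1. The plan's own figure.** The margin is stated as "lower limit of the 97.5% CI is above 0.67 (using 10% as non-inferiority margin and assuming a reference proportion of 0.5". Ten points below 0.5 gives (0.4/0.6)/(0.5/0.5) = 0.667, which rounds to 0.67. The margin reproduces. The documents give no Phase II sample size (only the cap of 300 in 14.8) and no power for the secondary tests, so there is nothing further to reproduce.

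**2. Error at the margin under dilution.** Suppose the true odds ratio is 0.67 and a share f of subjects give pairs carrying no lens difference.

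- From the documents: margin 0.67, so |ln 0.67| = 0.4005; one-sided 97.5% limit, so critical value 1.96.
- Assumed: f = 5% or 10%; N = 235 as an intermediate size and 300 as the cap; standard error of the log odds ratio 0.285 × √(60/N).
- Formula: error = P(Z > 1.96 − f × 0.4005/SE).

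| N | SE | f | shift | threshold | error |
|---|---|---|---|---|---|
| 235 | 0.144 | 5% | 0.139 | 1.821 | 3.4% |
| 235 | 0.144 | 10% | 0.278 | 1.682 | 4.6% |
| 300 | 0.127 | 5% | 0.157 | 1.803 | 3.6% |
| 300 | 0.127 | 10% | 0.314 | 1.646 | 5.0% |

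**3. A second model as a check.** Treat the rating as paired binary, with P1 at 0.50 and O1D at 0.67/1.67 = 0.401, and within-subject correlation from 0 to 0.5 (assumed). With f = 5% showing no difference, the O1D proportion is 0.95 × 0.401 + 0.05 × 0.50 = 0.406, an odds ratio of 0.684. With f = 10% it is 0.698. Error = Φ((ln OR − ln 0.67)/SE − 1.96). At N = 300 this gives 3.3% to 3.7% for f = 5% and 4.4% to 5.4% for f = 10%, across the correlation range. At N = 150 and f = 10% it gives 3.7% to 4.4%.

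If the deviators had instead worn the two lenses in swapped order, the odds ratios would be 0.698 and 0.726, and the errors at N = 300 would be 4.3% to 5.3% and 7.1% to 10.2%. Swapping is the harsher case. The documents give no rate for it, and 5% to 10% of subjects swapped would be a conduct failure of another order.

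**4. Which items the mechanism reaches.**

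- *Group 4.* Rated after about a week of wear (steps 2.7 and 4.7), so both wear deviations and wrong-lens errors can act.
- *Group 3.* The items concern the first minute after insertion. The post-fit questionnaire is step 1.23 or 3.12, before dispensing at 1.27 or 3.16, so days without wear come after the rating. Of the other Table 5 categories, a late visit has no clear diluting effect and an unanswered item is simply missing. Only a wrong-lens error remains.

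**5. Cost in power of a Per-Protocol requirement.** Take a true odds ratio of 1, N = 300 and Per-Protocol at 90% of ITT (assumed). Power = Φ(0.4005/SE − 1.96), with SE = √(2(1 − r)/(0.25n)) and n = 300 or 270. For the requirement that both limits pass, treat the two estimates as correlated at √0.9 = 0.949, since one set lies inside the other.

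| r | ITT alone | Per-Protocol alone | both |
|---|---|---|---|
| 0 | 0.689 | 0.643 | 0.616 |
| 0.3 | 0.834 | 0.794 | 0.776 |
| 0.5 | 0.934 | 0.908 | 0.900 |

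The Per-Protocol test alone loses 2.6 to 4.6 points per item against ITT. Requiring both loses 3.4 to 7.3 points.

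**The case against.** Several points against the concern have force.

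- *The dilution model is severe.* It treats a deviator's whole pair as noise. Handling items ask about putting lenses on and taking them off; subjects insert the study lenses themselves at fitting and must arrive at follow-up wearing them. Someone who missed three days has still handled the lens. Section 8.2 also calls for withdrawal of subjects who do not keep to the wear schedule, which limits how many complete diluted pairs reach the analysis. This stands, and is why 5% to 10% wholly uninformative pairs is an upper-end assumption.
- *Per-Protocol is not automatically the safer set.* For Group 3, subjects rate insertion before the check that comfort is acceptable (steps 1.25 and 3.14). Those not dispensed for poor comfort are withdrawn, and Per-Protocol then drops their ratings while ITT keeps them. If such failures were commoner with O1D, Per-Protocol would favour O1D. This stands and decides the Group 3 part of the fix.
- *Reach is limited.* Under 14.4, Groups 3 and 4 are tested only after superiority on all three primary endpoints and on Groups 1 and 2. That limits how often the issue arises, but comfort superiority says nothing about handling, so it does not remove the issue once the tests are reached.
- *A stand-alone SAP is promised in 14.1.* It may contain a Per-Protocol analysis. None of its text is available here, so this can be neither confirmed nor excluded.

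A reader might also infer that using Per-Protocol in Phase I and ITT in Phase II is an inconsistency in itself. The documents do not support that: 14.2 says Phase I was not powered for non-inferiority, and 14.8 uses it to decide on continuation and sample size. The contrast shows only that the set is available.

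**Conclusion.** The gap is real but modest. As specified, non-inferiority on handling is decided on ITT alone, and no planned test would show whether deviations had helped the claim. Under the upper-end assumption of 5% to 10% wholly uninformative pairs, the per-item error at the margin is about 3.4% to 5.0% instead of 2.5% at N = 235 to 300. The share, the standard error and N = 235 are assumptions; only the margin, the confidence level and the cap of 300 come from the documents.

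Two stronger readings are not supported. One is that deviations will pull the odds ratio towards 1: this is a tendency, and no deviation rate is given. The other is that all five non-inferiority items are exposed alike: wear deviations cannot dilute Group 3, and for those items Per-Protocol could be the less cautious set.

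**What to change.** In 14.1 and 14.6, and in the stand-alone SAP before database lock:

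- **Group 4:** test each handling item on both ITT and Per-Protocol, and conclude non-inferiority only if both lower limits exceed 0.67. Requiring both guards against dilution in ITT and selection in Per-Protocol.
- **Group 3:** keep ITT as the deciding set, report Per-Protocol as supportive, and list the subjects it drops because lenses were not dispensed.
- **Superiority tests:** keep ITT.

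Margin and alpha do not change. The cost is five model reruns on a set already defined and reviewed, plus the power loss shown above for each Group 4 item. That loss shrinks if fewer than 10% of subjects are excluded.
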